#### Renal Safety

Baseline estimated glomerular filtration rate (eGFR) will be summarized by treatment group for actual value and for baseline eGFR categories. Shift tables of eGFR category from baseline over the study, will be provided by treatment group. Shift tables of urine protein (negative/positive) from baseline over the study, will be provided by treatment group. Values of CK over the study will be summarized by treatment group and by baseline eGFR category. Finally, muscle-related AEs will be summarized by treatment group and by baseline eGFR category.

Clinical Endpoints

*Clinical endpoints* will be monitored and adjudicated by an independent blinded expert CEC for ongoing studies the ETC-1002 program. Adjudicated *clinical endpoints* will be summarized by event type and treatment group. Additional details regarding *clinical endpoints* and *clinical endpoint* definitions will be included in CEC charter.

Neurocognitive Events

Neurocognitive events will be identified and evaluated by routine safety monitoring of PE findings and AEs. Summarization of neurocognitive events will occur using prespecified Medical Dictionary for Regulatory Activities (MedDRA) terms and will be performed by SOC, severity, and relationship to study drug for each treatment group

Key Efficacy Endpoints

*Percent change from baseline to Week 12 or Week 24 in LDL-C, non-HDL-C, TC, apoB, and hs-CRP will be analyzed using analysis of covariance (ANCOVA), with treatment and randomization strata (patient's CV risk and baseline statin dose) as factors and respective baseline value as a covariate. The FAS will be used. Missing data for these endpoints will be imputed using multiple imputation taking account for treatment adherence.*

Other Efficacy Endpoints

*LDL-C, HDL-C, TG, TC, non-HDL-C, hs-CRP, and apoB values at other time points will be summarized and analyzed similarly to the key lipid endpoints. In addition, a summary using the FAS, excluding patients who received additional lipid-lowering therapy by that time point (by Week 24 for the Week 24 time point; by Week 52 for the Week 52 time point), will be provided. For both summaries, only observed case data will be used (no imputation for missing data).*

Additional post-randomization adjunctive lipid-modifying therapy

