### 5.3. Tertiary *Efficacy* Objectives

- *To assess percent change from baseline to Week 24 and to Week 52 in LDL-C in patients who do not receive adjunctive lipid-lowering therapy*
- *To assess high-density lipoprotein cholesterol (HDL-C), non-HDL-C, total cholesterol (TC), and TG at Weeks 12, 24, and 52*
- *To assess apoB and high-sensitivity C-reactive protein (hs-CRP) at Weeks 12, 24, and 52*

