#### **12.6.2. Other Efficacy Endpoints**

*Percent change or change in LDL-C, HDL-C, TG, TC, non-HDL-C, hs-CRP, and apoB values at other protocol-scheduled time points will be analyzed similarly using the ANCOVA model. The FAS will be used, with patients included in their randomized group, regardless of the treatment they actually received. No imputation for missing data will be performed.*

*For each parameter at each time point, the value of the parameter and the percent change from baseline in the parameter will be summarized by treatment group.*

*In addition, percent change from baseline to Week 24 and to Week 52 LDL-C will be analyzed with patients in the FAS who did not receive additional lipid-lowering therapy by that time point (by Week 24 for the Week 24 analysis; by Week 52 for the Week 52 analysis) included in the analyses. Only observed case data will be used (no imputation for missing data). Output from each time point will include the LSM and SE for each treatment group, as well as the placebo-correct LSM, 95% CI and p-value.*

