3.1 Objectives

The primary objective for this study is to evaluate the long-term safety and tolerability of ETC-1002 (bempedoic acid) versus placebo in high cardiovascular (CV) risk patients with hyperlipidemia (with underlying heterozygous familial hypercholesterolemia [HeFH] and/or atherosclerotic cardiovascular diseases [ASCVD]) who are not adequately controlled with their maximally tolerated lipid-modifying therapy.

The secondary objective is to assess the efficacy as the percent change from baseline to Week 12 in low-density lipoprotein cholesterol (LDL-C). This is the primary efficacy endpoint.

The tertiary objectives are:

- To assess percent change from baseline to Week 24 and to Week 52 in LDL-C in patients who do not receive adjunctive lipid lowering therapy.
- To assess high-density lipoprotein cholesterol (HDL-C), non-HDL-C, total cholesterol (TC), and triglycerides (TG) values at Week 12, 24 and 52.
- To assess apolipoprotein B (apoB) and high-sensitivity C reactive protein (hsCRP) values at Week 12, 24, and 52.

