3.3.3 Other Efficacy Endpoints

Percent change or change in LDL-C, HDL-C, TGs, TC, non-HDL-C, hsCRP, and apoB values at other protocol-scheduled time points will also be evaluated as secondary efficacy endpoints (See Section 5.3 for more information)

Proportion of patients achieving LDL-C < 70 mg/dL at week 12, 24 and 52 will be evaluated.

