5.3.3 Other Efficacy Endpoints

Percent change from baseline to week 52 in LDL-C will be analyzed using the ANCOVA method as described in section 5.3.1., using observed data (no imputation for missing data).

In addition, the same endpoint will be analyzed with patients in the FAS who did not receive additional lipid-lowering therapy by that time point (by week 24 and 52). Only observed case data will be used. Non-HDL-C, TC, ApoB and hsCRP at week 24 and 52 will be analyzed similarly using observed data.

The proportion of patients achieving LDL-C < 70 mg/dL at week 12, 24, and 52 will be summarized by treatment group and compared by Chi-sq test or fisher exact test. Only observed data will be used, i.e. the denominator will be number of patients who have LDL-C value at perspective time point.

TGs and HDL-C values at week 12, 24 and 52 will be summarized based on the FAS. For each parameter at each time point, the value of the parameter and the percent change from baseline in the parameter will be summarized by treatment group.

In cases where triglycerides (TGs) is >400 mg/dL or LDL-C is \leq 50 mg/dL, a measured LDL (LDL-M) will be used instead of LDL-C for the analysis of that time point. If both values are available, LDL-M will be used.

Baseline for each lipid is defined as the average of S1 (week -2) and predose Day 1/Week 0 values (the last two non-missing values on or prior to Day 1) with exception for apoB and hsCRP, for which predose Day 1 value will be used.

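### The SAP replaces the protocol's between-arm ANCOVA of HDL-C and triglycerides with by-arm summaries and does not declare the change

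*SAP*

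**What the plan says.** Both documents keep the same tertiary objective. Protocol 5.3 reads "To assess high-density lipoprotein cholesterol (HDL-C), non-HDL-C, total cholesterol (TC), and TG at Weeks 12, 24, and 52", and SAP 3.1 repeats it as "To assess high-density lipoprotein cholesterol (HDL-C), non-HDL-C, total cholesterol (TC), and triglycerides (TG) values at Week 12, 24 and 52".

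Protocol 12.6.2 names the parameters, "Percent change or change in LDL-C, HDL-C, TG, TC, non-HDL-C, hs-CRP, and apoB values", and says that their "values at other protocol-scheduled time points will be analyzed similarly using the ANCOVA model". It uses the full analysis set (FAS) and imputes nothing. The protocol synopsis, under Other Efficacy Endpoints, has the same rule: "values at other time points will be summarized and analyzed similarly to the key lipid endpoints".

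SAP 3.3.3 carries the seven parameters over, says that their "values at other protocol-scheduled time points will also be evaluated as secondary efficacy endpoints", and refers to Section 5.3 for the method. In that section, 5.3.1 gives ANCOVA for LDL-C, non-HDL-C, total cholesterol (TC) and apoB, and a Wilcoxon test with Hodges-Lehmann estimates for hsCRP. SAP 5.3.3 extends analysis to LDL-C at Week 52 and to non-HDL-C, TC, apoB and hsCRP at Weeks 24 and 52, on observed data. For the other two parameters it says "TGs and HDL-C values at week 12, 24 and 52 will be summarized based on the FAS", and that "the value of the parameter and the percent change from baseline in the parameter will be summarized by treatment group".

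SAP 2 states that the SAP prevails where the two documents differ on analysis.

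**The concern.** HDL-C and TG are named in an objective of a randomised, placebo-controlled trial, and the protocol plans to estimate a treatment effect for them. Under the governing SAP the report would show two columns of descriptive statistics, with no pre-specified adjusted difference or interval. If someone later runs the ANCOVA, it will be post hoc with respect to the SAP, although the protocol had planned it. The change is also hard to notice. SAP 4.6 lists three changes from the protocol and the SAP's summary of changes lists sixteen items; neither includes this one.

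**Working it through.** **1. Which visits fall under the protocol's rule.** The step-down list (Protocol 12.6.1, SAP 5.3) contains LDL-C at Weeks 12 and 24, and non-HDL-C, TC, apoB and hsCRP at Week 12. It contains neither HDL-C nor TG. Every HDL-C and TG visit is therefore an other time point, and Protocol 12.6.2 assigns it to the ANCOVA.

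**2. What the SAP specifies at the objective's visits.**

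| Parameter in the tertiary objective | Week 12 | Week 24 | Week 52 |
|---|---|---|---|
| Non-HDL-C | ANCOVA | ANCOVA | ANCOVA |
| TC | ANCOVA | ANCOVA | ANCOVA |
| HDL-C | summary by arm | summary by arm | summary by arm |
| TG | summary by arm | summary by arm | summary by arm |

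SAP 5.3.3 uses separate verbs for analysing and summarising, so the descriptive reading is the natural one. The only other SAP text that reaches HDL-C and TG is descriptive too: the all-visit statistics and figure in 5.3.1 and the on-treatment by-visit summary in 5.3.4.

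**3. Weeks 4, 8 and 36.** Basic fasting lipids are drawn at these visits. Protocol 12.6.2 covers them with ANCOVA. The SAP names no model there for any basic lipid (LDL-C, HDL-C, non-HDL-C, TC, TG) and gives descriptive statistics only.

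**4. Does sample size give a reason to omit the contrast?** The documents state no effect size, SD or precision for HDL-C or TG; the sample size rests on adverse-event rates. The inputs from SAP 4.4 are 1300 and 650 randomised, 7.5% dropout at 6 months and 10.0% at 12 months.

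- The plan's own exposure figures reproduce. At 6 months, 1300 × 0.925 = 1202.5 and 650 × 0.925 = 601.25 (stated: 1,202 and 601). At 12 months, 1300 × 0.90 = 1170 and 650 × 0.90 = 585 (stated: 1,170 and 585).
- The unadjusted 95% CI half-width for a difference in mean percent change, with equal SD in both arms and n patients on placebo, is 1.96 × SD × √(1/n + 1/(2n)) = 1.96 × SD × √(1.5/n).
- At Week 52, n = 585: 1.96 × √(1.5/585) = 0.099 SD. At Week 24, n = 601: 0.098 SD. At full enrolment, n = 650: 0.094 SD, a lower bound for Week 12.
- For assumed SDs of percent change of 15, 20, 30, 40 and 50 points, the Week 52 half-widths are 1.5, 2.0, 3.0, 4.0 and 5.0 points.
- The Week 52 detectable difference at two-sided 0.05 is (1.960 + 0.842) × √(1.5/585) = 0.142 SD for 80% power and (1.960 + 1.282) × √(1.5/585) = 0.164 SD for 90% power.

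A modest difference could be estimated well, so lack of precision does not explain the omission.

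**The case against.** The case for leaving the plan alone has several parts, and much of it limits how far the point can be pushed.

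- **The whole objective is unanswered.** A reader might infer this, but non-HDL-C and TC in the same objective keep ANCOVA at Weeks 12, 24 and 52. Only the HDL-C and TG parts lose the comparison. The objective is tertiary, and the trial's primary objective is safety.
- **LDL-C at Weeks 4, 8 and 36 also drops out of an objective.** It does not. The LDL-C objectives name Weeks 12, 24 and 52, all of which keep ANCOVA. At the intermediate visits the SAP is silent on a model rather than expressly withdrawing one, and the gap is the same for every basic lipid.
- **Skewed TG will be described only by mean and SD.** This is not so. SAP 5.1 defines descriptive statistics to include the median and quartiles, and 5.3.1 plans a figure using median and interquartile range where appropriate.
- **The SAP discards all the precision.** This is also too strong. With n, mean and SD of percent change by arm, a reader can compute a crude difference and interval, and the half-widths above are exactly that crude calculation. What is missing is the pre-specified, stratum- and baseline-adjusted estimate.
- **The SAP breaks the rule of precedence.** It does not; the SAP is entitled to differ. The conflict with SAP 3.3.3 is also mild, because evaluating an endpoint can be read as describing it.

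Two things survive. The protocol's analysis was removed without being declared or justified. And no SAP section gives a between-arm estimate for either parameter, although a comparison of the proportion with LDL-C below 70 mg/dL, which the SAP's own change log calls exploratory, does get a between-arm test.

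**Conclusion.** The point holds for HDL-C and TG. Protocol and SAP differ on whether a treatment effect is estimated, the SAP's descriptive version governs, and the departure is undeclared. The loss is a pre-specified, baseline-adjusted difference from placebo with its interval, for two of the four parameters in one tertiary objective. Nothing in the primary safety evaluation, the primary or key secondary efficacy tests, the type I error control or the sample size changes.

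The size given, a half-width of about 0.099 SD at Week 52, assumes about 1170 and 585 observed values and equal SDs. The observed numbers may differ, because the plan's dropout rate concerns exposure to treatment and patients who stop treatment are asked to keep giving lipid samples. The conversion to 1.5 to 5.0 points uses assumed SDs only, and for TG a normal-theory half-width is only a rough guide if the distribution is skewed. The textual finding depends on none of these assumptions.

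**What to change.** In SAP 5.3.3, replace the summary-only sentence for these two parameters with an analysis:

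- Percent change in HDL-C at Weeks 12, 24 and 52: the 5.3.1 ANCOVA (treatment, IWRS stratum, baseline) on observed FAS data.
- Percent change in TG at the same weeks: the same ANCOVA, moving to the Wilcoxon test with Hodges-Lehmann estimate and interval already used for hsCRP if the ANCOVA assumptions are severely violated. SAP 5.3.1 already has a fallback of this kind; naming the method for TG closes the choice.
- Report the difference from placebo, its 95% CI and a nominal p-value, stated to lie outside the step-down procedure.

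For Weeks 4, 8 and 36, either follow Protocol 12.6.2 for all basic lipids or list their descriptive-only treatment in SAP 4.6.

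If the sponsor prefers to keep HDL-C and TG descriptive, SAP 4.6 should say so with a reason, and SAP 3.3.3 and Protocol 12.6.2 should be brought into line.

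The cost is a few lines of SAP text and extra runs of an existing model on data already collected. The change should be made before database lock so that the analysis counts as pre-specified.

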5.3.4 Sensitivity Analysis for Efficacy Endpoints

- A sensitivity analysis for primary and key secondary endpoints included in the step-down procedure will be performed using the ANCOVA model with derived stratum instead of IWRS randomized stratum. For details of how the stratum are derived using concomitant medication and medical history, please see Appendix 3.
- The observed case data only (no imputations for missing data) analyses will also be used for sensitivity analyses for primary and key secondary endpoints. Observed data analysis will be conducted using FAS.
- On-treatment analysis will be using data collected during the treatment period only, i.e. up to the date of last dose of IMP +7 days (e.g. any efficacy data collected after 7 days post last dose of IMP will be excluded for efficacy analysis). On-treatment analysis will be conducted using SP for primary and key secondary endpoints
- By-visit summary for all efficacy endpoints (LDL-C, non-HDL-C, TC, ApoB, hsCRP, HDL-C and TGs) using on-treatment approach will be provided for both conventional and standard units.

5.3.5 Subgroup Analysis for Efficacy Endpoints

The LDL-C efficacy endpoints at week 12 will be analyzed within subgroups described in section 5.2.5. No imputation will be performed on missing data for subgroup analyses. Subgroups based on stratification factors will be derived from corresponding eCRFs such as targeted CV history or concomitant statin medication.

A forest plot of treatment effect for the LDL-C endpoint within each subgroup will be provided.

5.4 Primary Safety Endpoints and Analyses

The safety and tolerability of ETC-1002 will be assessed by examination of TEAEs (including muscle related events and other AESI), physical exams, vital signs, electrocardiograms (ECGs), clinical laboratory values (serum chemistry, hematology, coagulation and urinalysis), and weight. These endpoints identified in Section 3.2 with exception of PK-related endpoints, will be addressed as a result of the analysis description. All patients included in the SP will be evaluated in the safety analyses.

Unless otherwise stated, descriptive summaries will be displayed by treatment group actually received and based on the SP.

5.4.1 Adverse Events (AEs)

AEs will be coded using the Medical Dictionary for Regulatory Activities (MedDRA) Version 18.1 or later and will be categorized by system organ class (SOC) and preferred term (PT). Patients with AEs that are ongoing at study completion or study withdrawal must be followed until resolution or for 30 days after the last study visit, whichever comes first. Summary tables will focus on TEAEs; however, listings will include all AEs (with non-TEAEs flagged).

In summary tables, TEAEs will be counted as “Not Related” if relationship to IMP was recorded as ‘Not Related’ or ‘Unlikely’. Events will be counted as “Related” if relationship to IMP was recorded as ‘Possible’, ‘Probable’, ‘Definite’ or if relationship to IMP is missing.

The severity of the AE will be characterized as mild, moderate, or severe, to the following definitions:

- Mild: Events are usually transient and do not interfere with the patient’s daily activities
- Moderate: Events introduce a low level of inconvenience or concern to the patient and may interfere with daily activities
- Severe: Events interrupt the patient’s usual daily activity, are incapacitating with inability to do usual activities, or significantly affect clinical status and warrant intervention and/or close follow-up

Overviews of TEAEs will include total number of TEAEs and patient incidence of TEAE, TE SAE, related TEAE, related TE SAE, AESI, withdrew due to TEAE, Fatal Confidential

TEAE. Individual TEAE summary will be presented by treatment group containing the following counts and percentages for:

- patients with TEAEs
- patients with TEAEs by PT
- patients with TEAEs by SOC, PT and maximum severity
- patients with treatment-related TEAEs
- patients with treatment related TEAEs by PT
- patients with treatment related TEAEs by SOC, PT and maximum severity
- patients with treatment-emergent serious adverse events (TE SAEs)
- patients with TE SAEs by PT
- patients with TE SAEs by SOC, PT and maximum severity
- patients with treatment-related TE SAEs
- Fatal AEs by SOC and PT
- withdrawal from IMP due to TEAEs

Patient incidence (percent of patients experiencing the AE) will be provided for overall TEAE, treatment related TEAE, TE SAE, treatment related TE SAE, and AESI.

The TEAE, related TEAE, TE SAE, and AESI summaries by SOC and PT and maximum severity will be provided for relevant subgroups described in 5.2.5 with the exception of baseline LDL category.

The AE overview summaries will count a patient at most once in each AE category (at the “highest/most extreme” designation of each category regardless of preferred term) and percentages will be based on the total number of patients in the safety population.

In addition to a comprehensive listing of all AEs (with non-TEAEs flagged), separate listings will be generated for SAEs, AEs resulting in withdrawal of IMP, and AEs with a fatal outcome.

5.4.2 Adverse Events of Special Interest

Adverse events of special interest (AESI) will be identified based a pre-defined list of prefer terms provided by the sponsor (Appendix 2).

AESI will be presented in a listing and summarized by SOC, PT and treatment group.

In addition to adverse events, AESI is also being evaluated based on safety lab parameters. The details are provided in 5.4.6.

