5.4.6 Laboratory Evaluations

Continuous laboratory parameters (serum chemistry, hematology, coagulation (only at screening after amendment 3 and for those patients receiving anti-coagulation), urinalysis, urinalysis [microscopic]) listed in Table 4; fasting serum glucose, and HbA1c will be summarized using descriptive statistics for the observed value and the change from baseline by history of diabetics. Missing values for any of the laboratory evaluations will not be imputed; that is, only observed case data will be used. Baseline is defined as the last value prior to the first dose of study medication. Categorical urinalysis data will be listed, but will not be summarized.

As part of the AESI evaluation, below safety lab abnormality will be summarized by treatment group. All post-baseline lab values are being considered. Further details are provided in Section 5.4.6.1 through 5.4.6.4.

- ALT or AST (> 3x ULN and >5xULN)
- TB (> 2x ULN)
- Potential Hy's Law case: (ALT and/or AST > 3xULN with concurrent TB > 2xULN)
- CK (> 5x ULN) and (>10x ULN)
- Fasting Serum Glucose (mg/dL) (≤ 50 , and ≥ 126) by history of diabetics
- HbA1C ($\geq 6.5\%$) by history of diabetics
- Creatinine (change from baseline for >1 mg/dL)
- eGFR (< 15 mL/min/1.73m², 15 < 30 mL/min/1.73m²)
- Hgb (g/dL) (decrease from baseline for ≥ 2 g/dL)
- Hgb (<8 g/dL)

Table 4: Clinical Laboratory Parameters (Safety)

Hematology 
 • Hematocrit (Hct) • Hemoglobin (Hgb) • Mean corpuscular hemoglobin (MCH) • Mean corpuscular hemoglobin concentration (MCHC) • Mean corpuscular volume (MCV) • Platelet count • Red blood (RBC) cell count • White blood (WBC) cell count with differential (absolute and %) 	Blood Chemistry (serum, fasting) 
 • Albumin (Alb) • Alkaline phosphatase (Alk-P) • Alanine aminotransferase (ALT; SGPT) • Aspartate aminotransferase (AST; SGOT) • Blood urea nitrogen (BUN) • Calcium (Ca) • Carbon dioxide (CO₂) • Chloride (Cl) • Creatinine • Creatine kinase (CK) • Glucose • Lactate dehydrogenase (LDH) • Phosphorus • Potassium (K) • Sodium (Na) • Total and direct bilirubin (TB) • Total protein • Uric acid

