Appendix 2: Adverse Event of Special Interest (AESI)

Adverse Event Terms per Protocol	Associated MedDRA Preferred Terms
Creatine kinase elevations	Blood creatine phosphokinase abnormal
Creatine kinase elevations	Blood creatine phosphokinase increased
Creatine kinase elevations	Blood creatine phosphokinase MM abnormal
Creatine kinase elevations	Blood creatine phosphokinase MM increased
New onset or worsening diabetes mellitus	Blood glucose abnormal
New onset or worsening diabetes mellitus	Blood glucose increased
New onset or worsening diabetes mellitus	Diabetes mellitus
New onset or worsening diabetes mellitus	Diabetes mellitus inadequate control
New onset or worsening diabetes mellitus	Diabetic ketoacidosis
New onset or worsening diabetes mellitus	Glucose tolerance impaired
New onset or worsening diabetes mellitus	Glucose urine present
New onset or worsening diabetes mellitus	Glycosuria
New onset or worsening diabetes mellitus	Glycosylated haemoglobin increased
New onset or worsening diabetes mellitus	Hyperglycaemia
New onset or worsening diabetes mellitus	Impaired fasting glucose
New onset or worsening diabetes mellitus	Ketoacidosis
New onset or worsening diabetes mellitus	Ketosuria
New onset or worsening diabetes mellitus	Ketosis
New onset or worsening diabetes mellitus	Type 2 diabetes mellitus
New onset or worsening diabetes mellitus	Urine ketone body present
Hepatic disorders	Alanine aminotransferase abnormal
Hepatic disorders	Alanine aminotransferase increased
Hepatic disorders	Aspartate aminotransferase abnormal
Hepatic disorders	Aspartate aminotransferase increased
Hepatic disorders	Blood bilirubin abnormal
Hepatic disorders	Blood bilirubin increased
Hepatic disorders	Hepatic enzyme abnormal
Hepatic disorders	Hepatic enzyme increased
Hepatic disorders	Hypertransaminaseaemia
Hepatic disorders	Liver function test abnormal
Hepatic disorders	Liver function test increased
Hepatic disorders	Transaminases abnormal
Hepatic disorders	Transaminases increased
Hypoglycemia	Blood glucose abnormal
Hypoglycemia	Blood glucose decreased
Hypoglycemia	Hypoglycaemia
Hypoglycemia	Hypoglycaemic coma
Hypoglycemia	Hypoglycaemic encephalopathy
Hypoglycemia	Hypoglycaemic seizure
Hypoglycemia	Shock hypoglycaemic
Metabolic acidosis	Metabolic acidosis
Muscular disorders	Muscular weakness
Muscular disorders	Muscle necrosis

Muscular disorders	Muscle spasms
Muscular disorders	Myalgia
Muscular disorders	Myoglobin blood increased
Muscular disorders	Myoglobin blood present

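### AESI adverse events are tabulated by SOC and PT plus one pooled incidence, never by the eight Appendix 2 concerns, so no planned table counts patients with at least one AE in a multi-term concern

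*SAP*

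**What the plan says.** SAP 5.4.2 says that AESI "will be identified based a pre-defined list of prefer terms provided by the sponsor (Appendix 2"). The left-hand column of that appendix, headed "Adverse Event Terms per Protocol", assigns each term to one of eight concerns: creatine kinase elevations, new or worsening diabetes, hepatic disorders, hypoglycemia, metabolic acidosis, muscular disorders, neurocognitive/neurologic disorders and renal disorders.

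The planned AE output does not follow that column:

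- SAP 5.4.2: "AESI will be presented in a listing and summarized by SOC, PT and treatment group".
- SAP 5.4.1, overall: patient incidence "will be provided for overall TEAE, treatment related TEAE, TE SAE, treatment related TE SAE, and AESI", that is, one AESI figure.
- SAP 5.4.1, subgroups: "AESI summaries by SOC and PT and maximum severity will be provided for relevant subgroups".

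Two other parts of the SAP are organized closer to the concerns. Section 5.4.6 states "As part of the AESI evaluation, below safety lab abnormality will be summarized by treatment group", with details in 5.4.6.1 to 5.4.6.4. Section 5.4.3 summarizes muscle-related events from the AE CRF by SOC, PT and maximum severity.

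The protocol synopsis, under Neurocognitive Events in the statistical methods, says: "Summarization of neurocognitive events will occur using prespecified Medical Dictionary for Regulatory Activities (MedDRA) terms", by SOC, severity and relationship for each arm. It also plans an AE summary of new-onset diabetes by arm.

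**The concern.** Each concern is a clinical question with several terms that can express it. The natural readout is how many patients in each arm had at least one such event, each counted once. The planned rows sit on either side of that level: single terms, where events in one concern may be scattered, and a pooled figure, where all eight concerns are mixed. AEs belong to the primary safety endpoint (SAP 3.2), so a difference confined to one concern could be present in the data and yet be hard to see in the tables.

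**Working it through.** **Step 1. Count Appendix 2 and match each concern to its planned by-arm output.**

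| Concern | Term rows | Laboratory output (SAP 5.4.6 and subsections) | AE output specific to the concern |
|---|---|---|---|
| CK elevations | 4 | CK above 5x and 10x ULN | none |
| Diabetes | 16 | glucose ≥126 mg/dL, HbA1C ≥6.5%, shift tables | none in SAP; synopsis plans one for new onset |
| Hepatic | 13 | ALT or AST above 3x and 5x ULN, TB above 2x ULN, potential Hy's law | none |
| Hypoglycemia | 7 | glucose ≤50 mg/dL | none |
| Metabolic acidosis | 1 | none | its own PT row |
| Muscular | 14 | CK, as above | SAP 5.4.3, CRF-based, by SOC and PT |
| Neurocognitive | 6 | none | none in SAP; synopsis plans one |
| Renal | 17 | creatinine rise above 1 mg/dL, eGFR bands and shifts | none |

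Total: 4 + 16 + 13 + 7 + 1 + 14 + 6 + 17 = 78 rows. Blood glucose abnormal appears under both diabetes and hypoglycemia, so there are 77 distinct terms.

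**Step 2. See whether the count can be rebuilt from the planned tables.** A patient with two terms in one concern appears in two PT rows. The number with at least one event therefore lies anywhere between the largest PT row and the sum of the rows. If, say, each of the six neurocognitive rows showed 4 patients in an arm (assumed), the concern total could be from 4 to 24. The rule in SAP 5.4.1 that a patient counts at most once applies to the AE overview, where AESI is a single category, so it yields the pooled figure only. No sentence says that an SOC subtotal corresponds to a concern.

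**Step 3. Illustrate the size.** SAP 4.4 gives the arm sizes, 1300 and 650. With p1 and p0 the active and placebo proportions, SE(log RR) = √[(1−p1)/(1300·p1) + (1−p0)/(650·p0)], and the limits are RR × exp(±1.96·SE).

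The SAP's own row reproduces: at 0.5% vs 1.0%, SE = √(0.995/3.25 + 0.99/13) = 0.618, giving 0.60 to 6.72 (stated 0.6 to 6.7). Its other three intervals also reproduce to one decimal.

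Now assume a concern at 2% on placebo and 4% on active:

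- One concern row: SE = √(0.98/13 + 0.96/52) = 0.306, so RR 2.0 (1.10 to 3.65).
- Split evenly over six terms with no patient in two (0.333% vs 0.667%): SE = √(0.9967/2.167 + 0.9933/8.667) = 0.758, so each row has RR 2.0 (0.45 to 8.84).

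As an index of visibility, two-proportion power at two-sided 0.05 is Φ[(d − 1.96·SE0)/SE1], where d is the difference and SE0 and SE1 are its pooled and unpooled standard errors:

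| Assumed placebo rate, RR 2 | One concern row | Each of 3 terms | Each of 6 terms |
|---|---|---|---|
| 1% | 36% | 13% | 7% |
| 2% | 66% | 24% | 13% |
| 3% | 84% | 36% | 18% |
| 5% | 98% | 57% | 30% |

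If one term carries nearly all events in a concern, its PT row shows most of the signal and little is lost.

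**The case against.** The strongest reply is that much of the ground is covered elsewhere. The sentence in SAP 5.4.2 after the one on tabulation extends the AESI evaluation to laboratory parameters, and 5.4.6 delivers these by arm. All 13 hepatic terms are laboratory findings, and the combined ALT-or-AST criterion avoids double counting. Metabolic acidosis needs no grouping, and muscle events have their own summary. This stands. A reader might infer that no table gives any by-arm incidence for hepatic, renal or diabetic concerns; the documents do not support that. What remains is that threshold counts are not AE counts. They omit acute kidney injury, renal failure, gout and diabetes mellitus as reported diagnoses, and no threshold exists for neurocognitive events.

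A reader might also infer that the SAP cancels the synopsis summaries of neurocognitive and new-onset diabetes AEs. It does not say so: the SAP prevails only where the documents differ, and its list of changes (4.6) does not drop them. They are simply not carried into the SAP, and as planned they are themselves SOC-based. The AESI text in protocol 12.5 is redacted, so the protocol's own layout cannot be judged.

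It is tempting to add that SOC rows cut across the concerns. Neither document gives SOC assignments, so that argument is not used here.

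Finally, SAP 5.4 plans descriptive safety summaries, and the AESI listing would let someone count by hand. Both are fair: the power figures describe no planned test, and the count is missing from the tables, not from the data.

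**Conclusion.** The point holds in a limited form. For concerns with more than one term, the SAP plans no by-arm number of patients with at least one AE, and overlapping PT rows cannot supply it. The practical gap is greatest for neurocognitive events, then for renal and diabetes diagnoses. It is small for hepatic events and absent for metabolic acidosis.

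This is a matter of table layout. It biases no estimate and affects no error rate. The size shown depends on assumed incidences, a doubling of risk and an even split over terms. A reader might take those figures to mean that the trial would miss a signal, but they are illustrations and not properties of the plan. The improvement is worth making because the grouping already exists and it sharpens the primary safety readout.

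**What to change.** In SAP 5.4.2, keep the SOC/PT table and the pooled AESI incidence, and add: *n (%) of patients with at least one treatment-emergent AESI by Appendix 2 category, and by PT within category, by treatment group, counting each patient once per category*. Use the same layout for the AESI subgroup tables in 5.4.1.

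State before unblinding how Blood glucose abnormal is assigned, for example by the direction of the glucose value on the record. Otherwise one event would count under two opposite concerns.

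Cost: SAP wording, one table shell and one assignment rule. No new data are needed.
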